1. Developing a novel technology-based intervention for anxiety and depressive symptoms among those receiving medication treatment for OUD.
2. Evaluating the feasibility of a technology-based intervention for anxiety and depressive symptoms among persons receiving treatment for OUD.
3. Evaluating the efficacy of a technology-based intervention for anxiety and depressive symptoms among persons with OUD.
4. Evaluating the efficacy of a technology-based intervention treating anxiety and depressive symptoms on cravings and opioid use among persons receiving medication treatment for OUD.

2. Objectives and Hypotheses

Aim 1: To test the feasibility and acceptability of the digital intervention designed to treat anxiety and depressive symptoms among persons receiving medication treatments for OUD.

Hypothesis 1: The digital intervention will show feasibility based on the ability to recruit participants (N = 40 within the digital intervention + medication treatment, N = 40 with medication treatment) and demonstrate acceptability of the application with greater than 50% of the intervention sessions completed on average by the treatment group.

Aim 2: To test the efficacy of a digital intervention targeting anxiety and depressive symptoms among persons receiving medication treatment for OUD. Sixty participants receiving medication treatment for OUD will be randomized to receive a digital intervention to treat anxiety and depression (N = 30) or care as usual (N = 30) for a total of four weeks.

Hypothesis 2: The digital intervention app group will experience (a) greater symptom reduction in anxiety and depressive symptoms (based on self-report measures) and (b) decreased opioid cravings and use across a four-week period (based on self-report measures and urine tests).

3. Study Design

Describe all study procedures, materials, and methods of data collection:

Recruitment. A population of 3000 adults who are receiving medication treatment for OUD will be recruited from an online study based on Google Adwords and Facebook advertisements as online recruitment has been shown to be a viable and cost-effective recruitment method for opioid users (Marshall et al., 2018).

We would also like to expand our recruitment efforts to Reddit sub-pages as well. Previous researchers looking at opioid addiction have had success posting in the Reddit forums and we would like to also recruit using this platform.

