Analyses. To test feasibility for **Hypothesis 1**, we will determine whether we can achieve the targeted enrollment ($N = 80$) and whether the average number of digital sessions is significantly higher than 50% based on multilevel binomial test nesting individual session completion rates within persons. To test **Hypothesis 2**, the current proposal will use intent-to-treat analyses employing multilevel modeling to examine moderation of change across time from pre to post, and post to follow-up. Based on power analyses, we will be well-powered to test the effects of the intervention (3-5 data points per person \times 80 participants = 180-300 \times 80% adherence = 144-240 data points total).

5. Study Progress Monitoring

Note: appropriate monitoring may include periodic assessment of the following:

- data quality
- timelines
- recruitment and enrollment

Provide a description of the methods which will be used to determine the progress of the study, including periodic assessments of data quality, timelines, recruitment, and enrollment as appropriate:

Recruitment. A population of 3000 adults who are receiving medication treatment for OUD will be recruited from an online study based on Google Adwords advertisements as online recruitment has been shown to be a viable and cost-effective recruitment method for opioid users (Marshall et al., 2018). We are only recruiting from the US.

We will also recruit via Reddit forum as well. Please see the document with the example of the post we would be planning on using.

Six opioid-focused subreddits were initially identified. Subreddits were selected based on their topical focus and their popularity. All were devoted to discussion of opioid use or recovery. In September 2019, the number of Redditors subscribed to each subreddit ranged from 4,000 to 82,000 people. Each subreddit was monitored by multiple moderators, who ensured all posts follow the Reddit community guidelines and remain focused on the topic of interest. All moderators in each of the six subreddits will be contacted by the study team to obtain approval to post the survey description and hyperlink. Moderators will be sent a study information sheet and a link to view the study description.

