Does any part of this study involve the use of a placebo or procedures that are inconsistent with the standard of care?

No Yes

If Yes, explain how the use of placebo or non-standard of care therapy may affect risks for participants, addressing the following:

- The safety and efficacy of other available therapies
- The maximum total length of time a participant may receive placebo on study
- The greatest potential harm that may result from not receiving or delaying effective therapy
- Safeguards for the participants receiving placebo or non-standard of care therapy

n/a

9. Genetics

Does any part of the study involve genetic analysis of biological specimens?

No

Yes, the study is based on the premise that a link between a genotype or a biomarker and a specific disease or condition is clinically useful in predicting the development of that specific disease or condition.

Please complete the [Genetic Research Form](#) and upload it to the 'Supporting Documents' page in Rapport.

-OR -

Yes, the study is looking for an association between a genotype or a biomarker and a specific disease or condition, but at this point it is not clear if the genetic marker has predictive value. The uncertainty regarding the predictive value of the genetic marker is such that studies in this category will not involve referral of participants to genetic counseling; however, participants will be informed of genetic testing in the consent form. **Please comment:**

We ask participants to take urine samples throughout the course of the study. We will send participants urine tests to their physical address. Then we will ask participants to take pictures of the urine tests and send them to the research team. Participants will have access to their results, but the study team will not collect any physical bio samples, just pictures of the urine test results.

10. Equitable Participant Selection

a. Estimated number of participants at Dartmouth CPHS reviewed sites:

The research team hopes to enroll 80 participants

b. Provide a justification of the proposed sample size

Participants will be recruited from an online study based on Google Adwords and Facebook advertisements as online recruitment has been shown to be a viable and cost-effective recruitment method for opioid users (Marshall et al., 2018).

c. Define the target population:

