13. Financial impact on participants

a. List the tests, visits, and procedures performed for only research purposes and specify who will pay:

Note: Research procedures may not be billed to a health insurance plan

Participant Recruitment. A total of \$3,000 will be spent on online participant recruitment in the US only. We estimate a total cost of \$10 per participant to recruit 3000 participants, with an estimated enrollment of 2% of persons who complete the screen will enroll in the primary portion of the study.

Precision Dx 12-panel Urine Tests. The Precision Dx 12 Panel Cup test cups will cost a total of \$2,250.00 to purchase (we will need to purchase 300 units, with 25 units per case, we will need to purchase 12 cases with each case costing \$187.50). To save on shipping costs, the five tests will be mailed together to participants in one box. Participants will be asked to send a picture of the results label to save on shipping costs and so that no bodily fluids are traveling via mail. There will be an estimated \$720 in shipping costs.

Participant Remuneration: Participants will be paid \$15 for each pre, post, and follow-up questionnaire assessment and \$15 for each urine test (totaling \$120 per participant). Thus, the total cost requested for participant payment is \$7,200.

14. Compensation or Gifts

Please describe any payments, gifts or reimbursements participants will receive for taking part in the study:

Participants will be compensated via amazon giftcard for each component of the study they complete. They will receive 15 dollars for each questionnaire assessment they complete along with 15 dollars for each completed urine test. Compensation will be pro-rated if participants forget to complete any part of the study: The following information lays out the time points that participants will be compensated. Participants will not be compensated for completing the screening questionnaires.

Before the Digital Intervention: 30 dollars total

- 1) \$15 dollars for completing the self-assessment survey
- 2) \$15 dollars for providing the first urine (after 0 weeks) sample results.

After the Intervention is completed: 45 dollars total

- 1) 15 dollars for completing the post-intervention questionnaire
- 2) \$15 dollars for providing second urine sample (after 2 weeks)
- 3) \$15 dollars for providing third urine sample (after 4 weeks)

At the one-month follow-up: 45 dollars total

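### Section 13's recruitment budget, unit cost and screening number disagree tenfold, and even 3,000 screens at the stated 2% yield give 60 enrolled, not the 80 that Hypothesis 1 tests

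*Combined protocol and SAP*

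**What the plan says.** **Cost and yield.** Section 13 (Financial impact on participants, Participant Recruitment) allots $3,000 in all to online recruitment. Its next sentence gives the unit cost as $10, and states the basis, the quantity and the yield as follows: "per participant to recruit 3000 participants, with an estimated enrollment of 2% of persons who complete the screen will enroll".

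**Screening number.** The 3,000 also appears outside the budget. Section 3 (Study Design, Recruitment) says: "A population of 3000 adults who are receiving medication treatment for OUD will be recruited from an online study". Section 5 (Study Progress Monitoring) repeats it.

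**Enrolment target.** Hypothesis 1 in section 2 judges feasibility partly on recruiting 40 per arm, 80 in all. The Analyses paragraph of section 4 tests whether 80 is achieved, and section 10a also gives 80. Aim 2 in section 2, however, randomises 60 (30 per arm). Section 13 buys 300 urine cups at five per person and budgets $7,200 in payments at $120 per person.

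**Channels.** Sections 3 and 5 add recruitment through Reddit posts, for which no cost per person is given.

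**The concern.** Two adjacent sentences give a total, a unit price and a quantity that do not multiply out. The sentences are intact in the text, so extraction damage does not explain the mismatch.

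In many trials this would be a budgeting detail. Here recruitment is itself an outcome: Hypothesis 1 passes or fails partly on whether 80 people are enrolled. The screening number, the yield and the money available are therefore the planning basis for a tested result. If they are wrong, a shortfall cannot be interpreted. It could mean that eligible people are hard to find, that the money ran out, or that the planned number of screens was never enough for the target.

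**Working it through.** **Inputs.** From section 13: total $3,000, unit cost $10, 3,000 people, yield 2% of screen completers, 300 cups at five each, $7,200 at $120 each. From sections 3 and 5: 3,000 people. From sections 2, 4 and 10a: target 80. From Aim 2: 60.

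**Step 1: do the cost figures agree?** Total = unit cost x number.
- Holding $10 and 3,000: $10 x 3,000 = $30,000, not $3,000.
- Holding $3,000 and $10: $3,000 / $10 = 300 people, not 3,000.
- Holding $3,000 and 3,000: $3,000 / 3,000 = $1 per person, not $10.

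Each way round, the discrepancy is a factor of ten. Reading $10 as a cost per enrolled person does not help. It would give $600 for 60 people or $800 for 80, or 300 enrolled for $3,000, and none of these fits the plan.

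**Step 2: which figure has most support?** Expected enrolment = screens x yield.
- 3,000 x 0.02 = 60.
- Aim 2: 30 + 30 = 60.
- Cups: 300 / 5 = 60.
- Payments: $7,200 / $120 = 60.

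The path from 3,000 screens to 60 enrolled is therefore coherent with three other places in the plan. That points to the total or the unit cost as the likelier slip, but does not prove it.

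**Step 3: does the funnel reach the Hypothesis 1 target?**
- Expected from 3,000 screens: 60, which is 20 (25%) short of 80.
- Screens needed for 80 at 2%: 80 / 0.02 = 4,000.
- Yield needed for 80 from 3,000: 80 / 3,000 = 2.67%.
- Taking 2% as fixed and people as independent, the exact binomial probability of 80 or more from 3,000 is 0.7%.

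| Figures taken as right | Screens | Total | Expected enrolled at 2% |
|---|---|---|---|
| $3,000 and 3,000 people (unit cost $1) | 3,000 | $3,000 | 60 |
| $10 and 3,000 people | 3,000 | $30,000 | 60 |
| $3,000 and $10 | 300 | $3,000 | 6 |
| 80 enrolled, at $1 per screen | 4,000 | $4,000 | 80 |
| 80 enrolled, at $10 per screen | 4,000 | $40,000 | 80 |

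The third row counts paid advertising only, before any Reddit recruits. None of the first three rows, which use the plan's own figures, reaches 80.

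**The case against.** The strongest reply is that this is a slip in an ethics-form budget item, not in the design or analysis. The $10 and the 2% are both labelled estimates, and the Hypothesis 1 test asks only whether 80 were enrolled, with no tie to spend. Much of this stands, and it limits what can be claimed.

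A reader might infer that the trial can screen only 300 people, will enrol about 6, and so must fail its recruitment test by construction. The documents do not support that. It requires 3,000 to be the wrong figure, when 3,000 is the best supported of the three. No section says that recruitment stops after 300 screens. Reddit posts may add screens at no stated cost per person. The figure of 6 is what paid advertising alone would yield if the stated total and unit cost were both followed, and nothing more.

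A reader might also infer that the sample size justification in section 10b rests on the same faulty figures. It does not. That section says only that "online recruitment has been shown to be a viable and cost-effective recruitment method for opioid users" and contains no cost, screening number or yield. Whether this justifies a sample size is a separate question.

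The clerical argument does not dispose of the point. Once the cost slip is corrected, the gap between 60 and 80 remains, and 80 is the number tested.

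**Conclusion.** The point holds in two parts. First, the total, unit cost and screening number in section 13 contradict each other by exactly a factor of ten, and no reading removes this. The documents do not settle which is wrong. Second, the planned funnel supports 60 enrolled, not 80: it falls 25% short of the Hypothesis 1 target even if all 3,000 are screened.

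The first part is arithmetic and assumes only that $10 is a cost per person recruited to the screen, as the sentence reads. The second takes the stated 2% at face value and assumes that all 3,000 complete the screen. A modestly better yield, 2.67%, would close the gap, so a shortfall is what the plan's own figures predict and not a certainty. The correction should be made because recruiting 80 is a tested outcome.

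**What to change.** 1. In section 13, correct whichever of the total, the unit cost or the screening number is wrong, so that the three multiply out. State that the unit cost is per completed screen, if that is what is meant.
2. Then choose one of two routes.
   - Keep 80. Restate the screening number or the yield so that it supports 80 (4,000 screens at 2%, or 2.67% of 3,000), and carry any changed screening number into sections 3 and 5. Aim 2, the cups (80 x 5 = 400) and the payments (80 x $120 = $9,600) must then also move to 80.
   - Adopt 60 throughout, including Hypothesis 1, its test in section 4, and section 10a.
3. Report the observed number screened, the yield and the advertising spend beside the Hypothesis 1 recruitment result, so that a shortfall from spent budget can be told apart from infeasibility.

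**Cost.** The edits are wording, and the reporting adds no procedures. The downside is that the stated budget, yield or target becomes less favourable. If $10 per screen was meant, the advertising budget rises by $27,000 for 60 enrolled ($30,000 - $3,000) or by $37,000 for 80 ($40,000 - $3,000). If $1 was meant, 60 needs no more money and 80 needs $1,000 more. Keeping 80 at a 2% yield also means screening 1,000 more people.
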